4.2 Study Design and Scope

The study is a prospective, non-randomized, multi-center observational study designed to evaluate the diagnostic capabilities, indications, MRI scanning capabilities and clinical outcomes of patients implanted with an MRI compatible SJM pacemaker with a standard bradycardia pacing indication. Any patient that receives an Assurity MRI, Endurity MRI pacemaker (or

Template 90153521 Ver B Page 10 of 38

Study Name: BRADYCARE II

CIP

newer version) in the EMEA region or any patient that receives an Accent MRI, Assurity MRI, Endurity MRI or similar SJM MRI compatible device in the Asia-Pac region is eligible for enrollment in the study if they meet the inclusion/exclusion criteria.

Subjects will be followed for 12-months after pacemaker implant. Data will be collected at enrollment (within 30 days of device implant), 6 and 12-months post-implant and during any unscheduled follow-up visit. Remote follow-up using Merlin@home® and Merlin.net® is allowed for the 6-month visit as per the site's standard of care. However, subjects must have an in-office follow-up visit at 12-months post pacemaker implant. During the follow-up visits, arrhythmic episode diagnoses, device data, drug therapy, stored electrograms and if an MRI was done will be collected. All clinical events such as hospitalizations, emergency room visits, system revisions and external cardioversions will also be collected. All study data, including device data and stored electrograms will be sent to SJM via the electronic data capture (EDC) system.

This study will be offered to all subjects who are implanted with an SJM Brady MRI system in the EMEA and Asia-Pac region, therefore, the study population is expected to reflect the population of patients implanted with an SJM Brady MRI system in the EMEA and Asia-Pac region.

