4.3 Number of Subjects Required to be Included in the Study

Up to 2016 subjects will be enrolled in this study. No more than 200 enrollments (10% of the total study enrollment) will be allowed per center without prior SJM approval.

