4.5 Objectives

4.5.1 Objectives

The primary objective of the study is to characterize:

• complication rates in the general pacemaker patient population

The secondary objectives of the study are to characterize:

- Impact of usage of advanced features in pacemaker on the clinical outcomes
- MRI scanning capabilities and rates in pacemaker patients by country

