12.0 STATISTICAL CONSIDERATIONS

12.1 Statistical Design, Hypotheses, Method and Analytical Procedures

This is a post market, prospective, non-randomized observational study.

The primary endpoint will be summarized as counts and proportion of patients who experience complications. The 95% Binomial confidence interval for the complication rate at 1 year post implant will be reported as well.

Other data will be presented using appropriate summary statistics. All continuous data will be summarized using descriptive statistics, such as the number of non-missing data, mean ± standard deviation, median and range (minimum – maximum). Categorical data will be tabulated with counts and its percentage.

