12.2 Sample Size

The sample size calculation is based on the study design and primary objective of this study. The literature shows a complication rate of 12.2% at 1 year. Assuming the complication rate at one-year post implant is 12.2%, in order to obtain a confidence interval width of 3.1%, at least 1713 subjects will be required. Assuming a 15% attrition rate at one year, a total recruitment of 2016 subjects is needed.

Ver. A

Study Name: BRADYCARE II

CIP

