12.9 The Treatment of Missing, Unused or Spurious Data, Including Drop-Outs and Withdrawals

No imputation technique will be used, unless specified in the guidelines of the questionnaire data.

12.10 In Multi-Center Studies, the Minimum and Maximum Number of Subjects to be Included for each Center

This study is expected to enroll 2016 subjects in approximately 160 centers in the EMEA region and Asia-Pac region. It is desirable to have a balance of the subjects across participating centers; therefore, the maximum number of subjects to be included at each enrolling center is 200. Every effort will be made to promote recruitment; however, a low level of participation in the study could still occur, so the minimum number of subjects to be included at enrolling centers is one.

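### The binomial 95% CI and its 3.1% planned width make no allowance for differences between about 160 centers, so both overstate precision for the wider pacemaker population if centers differ

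*Combined protocol and SAP*

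**What the plan says.** The primary result is a count and a proportion with an interval (section 12.1): "The 95% Binomial confidence interval for the complication rate at 1 year post implant will be reported as well". Section 12.1 does not say whether this is the exact or the normal-approximation (Wald) form, and it includes no center term.

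Section 12.2 assumes a 12.2% one-year rate and says that "in order to obtain a confidence interval width of 3.1%, at least 1713 subjects will be required". With 15% attrition this becomes 2016 recruited.

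On centers, section 12.10 expects about 160. It says "It is desirable to have a balance of the subjects across participating centers", but the limits it sets are wide: "the maximum number of subjects to be included at each enrolling center is 200" and "the minimum number of subjects to be included at enrolling centers is one". Section 4.3 makes the upper limit conditional: "No more than 200 enrollments (10% of the total study enrollment) will be allowed per center without prior SJM approval".

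On the target, the primary objective in section 4.5.1 concerns "complication rates in the general pacemaker patient population", and section 4.5.2 names the same population for the outcome measure. Section 4.2 adds that "the study population is expected to reflect the population of patients implanted with an SJM Brady MRI system in the EMEA and Asia-Pac region".

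Section 12.7 stratifies reporting by country and region. No section mentions an ICC, a design effect, a robust variance or a center effect for the overall interval.

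**The concern.** A binomial interval treats every subject as an independent draw from the target population. If implant complication rates differ between centers, subjects from the same center resemble each other, and 1713 subjects in 160 centers carry less information about patients elsewhere than 1713 independent subjects would.

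Whether this matters depends on the target. For the rate in the enrolled centers alone, the binomial interval is not too narrow for this reason. The plan, however, states a wider target, and for that target the between-center variance belongs in the interval. Stratifying by country or region does not put it there.

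The interval is the only statement of precision for the primary result, and its width is the only basis for the sample size. If centers differ, both claim more precision than the data support for the population named in the objective.

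**Working it through.** **Inputs from the documents.** Rate p = 0.122, full width w = 0.031, 1713 evaluable, 15% attrition, 2016 recruited (section 12.2); about 160 centers, 1 to 200 subjects each (section 12.10).

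**Reproducing the plan's figures.** With the Wald width for independent subjects, n = 4 × 1.96² × 0.122 × 0.878 / 0.031² = 1712.7, so 1713. Then 1713 / 0.85 = 2015.3, so 2016. Both match with a design effect of exactly 1, so the plan has no allowance for centers.

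**Assumed inputs.** The documents give neither an ICC nor a distribution of center sizes. I take ICC = 0.005, 0.01 and 0.02. The between-center SD is √(ICC × 0.122 × 0.878), which is 2.3, 3.3 and 4.6 points. Under a beta distribution, the middle 95% of center rates is then about 8–17%, 7–19% and 5–23%. Four size patterns are considered:
- equal centers, mean 1713 / 160 = 10.706;
- center sizes with a coefficient of variation (CV) of 1;
- one center at the cap (200 × 0.85 = 170 evaluable), the other 159 equal;
- five centers at the cap, the other 155 equal.

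**Formulas.** With n_k subjects in center k and N = 1713:
- S = Σn_k² / N, which equals (1 + CV²) × 10.706
- DE = 1 + (S − 1) × ICC
- width = 3.10 × √DE
- approximate true coverage of the nominal 95% Wald interval = 2Φ(1.96 / √DE) − 1

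Values of S:
- equal: 10.706
- CV 1: 2 × 10.706 = 21.41
- one at cap: (170² + 1543² / 159) / 1713 = 25.61
- five at cap: (5 × 170² + 863² / 155) / 1713 = 87.16

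**Results at ICC 0.005 / 0.01 / 0.02.**

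| Center sizes | DE | Width needed (points) | Wald coverage (%) |
|---|---|---|---|
| Equal | 1.049 / 1.097 / 1.194 | 3.17 / 3.25 / 3.39 | 94.4 / 93.9 / 92.7 |
| CV 1 | 1.102 / 1.204 / 1.408 | 3.25 / 3.40 / 3.68 | 93.8 / 92.6 / 90.1 |
| One at cap | 1.123 / 1.246 / 1.492 | 3.29 / 3.46 / 3.79 | 93.6 / 92.1 / 89.1 |
| Five at cap | 1.431 / 1.862 / 2.723 | 3.71 / 4.23 / 5.12 | 89.9 / 84.9 / 76.5 |

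Beta-binomial simulation (10,000 or 20,000 runs per setting) agreed with the Wald coverage to within about half a point. The exact interval covered slightly better: 94.8 / 94.4 / 93.3% with equal centers and 94.3 / 93.2 / 91.2% at CV 1.

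**If all 2016 were analyzed.** The width under independence is 2 × 1.96 × √(0.122 × 0.878 / 2016) = 2.86 points. With equal centers of 12.6, DE = 1 + 11.6 × ICC, and the width is 2.94 / 3.02 / 3.17. The 3.1-point target allows DE up to (3.10 / 2.857)² = 1.177, so it holds up to ICC 0.177 / 11.6 = 0.015 with equal centers, or 0.177 / 24.2 = 0.007 at CV 1.

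**Does a center-based interval work?** I took a leave-one-center-out jackknife on the logit scale with t degrees of freedom N² / Σn_k² − 1 (159 for equal centers, 18.7 with five at the cap). Its simulated coverage at ICC 0 / 0.005 / 0.01 / 0.02 was:
- equal: 95.2 / 95.0 / 95.0 / 95.2%
- CV 1: 94.8 / 95.0 / 94.9 / 95.2%
- one at cap: 95.2 / 95.1 / 95.0 / 94.9%
- five at cap: 95.6 / 94.9 / 94.8 / 94.3%

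An ordinary cluster-robust logit interval with 159 degrees of freedom gave 93.5 / 92.2 / 92.0 / 91.0% with five at the cap, which is the reason for the reduced degrees of freedom.

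**The case against.** Sections 12.1 and 12.2 agree with each other, and nothing in the documents shows that centers differ. The size rests wholly on an assumed ICC. In the case nearest the plan's stated aim, balanced centers of about 11 evaluable subjects, the change is small. An exact interval at 209/1713 is already 3.16 points wide, so the unstated choice between exact and Wald matters about as much as an ICC of 0.005. Section 12.8 can be read as putting all 2016 subjects in the analysis, in which case the 3.1-point target survives part of the assumed range. Five centers at the cap would hold 1000 of 2016 subjects, the opposite of what section 12.10 wants. Centers are chosen for their ability to enroll (section 3.1), so no variance formula makes them a sample of all centers. Section 12.3 sets no pass/fail rule.

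Most of this stands, and it limits the size of the point. The five-center case is a stress case and should not set the severity. Analyzing all 2016 would rescue the width target, but the reported binomial interval would still omit center variation. Balance is an aim and not a constraint, and with ICC above 0 the interval is slightly too narrow even when centers are equal. Leaving the ICC out amounts to assuming it is zero without saying so. In a descriptive study the interval is the inferential result, so the lack of a decision rule does not excuse it.

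**Conclusion.** The concern holds, on the condition it states. The interval and the 3.1% width assume independent subjects, and for the population named in sections 4.2, 4.5.1 and 4.5.2 they understate uncertainty if complication rates vary between centers.

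With 1713 evaluable subjects and ICC 0.005 to 0.02, the effect is modest for balanced centers (at most about 0.3 points of width, coverage about 93 to 94%) and moderate at a center-size CV of 1 (at most about 0.6 points, coverage about 90 to 94%). It becomes large only with a concentration of enrollment that the cap permits but the plan does not intend. An ICC of 0.05 would imply center rates of about 2–30%, an extreme that nothing in the documents supports.

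The ICC and the size patterns are assumptions; at ICC 0 the plan's figure is right. The point estimate does not change and no decision rule is affected. This should be changed because the correction is cheap; it does not undermine the study.

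**What to change.** **Section 12.1.** Keep the crude proportion and the binomial interval, and add a 95% interval that allows for center. Omit each of the K centers in turn, take the logit of the rate in the rest, and use the jackknife variance (K − 1)/K × Σ(deviation from their mean)². Form logit(p̂) ± t × SE with N² / Σn_k² − 1 degrees of freedom, and back-transform. State that the binomial interval describes the enrolled centers and the added one is for the wider population. Report the estimated ICC and the distribution of center sizes.

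**Section 12.2.** Label 3.1% as the width under independence. Give the width over an assumed ICC range, for example 3.17–3.39 points (equal centers) and 3.25–3.68 (center-size CV 1) for ICC 0.005–0.02.

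**Limitation to state.** The added interval covers the sampling of centers only. It does not make centers selected for their ability to enroll representative.

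**Cost.** A few sentences and a few lines of code, using data already collected, with no extra patients. The stated precision looks slightly less favorable. If the ICC is truly 0, the added interval is a little wider than needed: 3.12 against 3.10 points with equal centers, 3.36 with five at the cap. With five at the cap and ICC 0.05, its coverage is still slightly low, at 93.4–93.5%.

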12.2 Sample Size

The sample size calculation is based on the study design and primary objective of this study. The literature shows a complication rate of 12.2% at 1 year. Assuming the complication rate at one-year post implant is 12.2%, in order to obtain a confidence interval width of 3.1%, at least 1713 subjects will be required. Assuming a 15% attrition rate at one year, a total recruitment of 2016 subjects is needed.

Ver. A

Study Name: BRADYCARE II

CIP

12.3 Pass/Fail Criteria to be Applied to the Results of the Clinical Study

This study is intended to characterize complication rates in the general pacemaker patient population. Therefore, Pass/Fail criteria do not apply to this study.

12.4 The Provision for an Interim Analysis, when Applicable

There are no pre-specified interim analyses planned for this study.

12.5 Criteria for the Termination of the Clinical Study on Statistical Grounds

There are no pre-specified criteria for terminating the clinical investigation on statistical grounds.

12.6 Procedures for Reporting any Deviation(s) From the Original Statistical Plan

Any deviations from the statistical analysis plan will be documented.

12.7 The Specification of Subgroups for Analysis

Stratified reporting/analysis will be performed by countries/ regions (EMEA/Asia-Pac).

12.8 Procedures that Take into Account All the Data

All subjects who have signed a Patient Informed Consent (PIC) will be considered enrolled in the study, hence are eligible for the primary analysis. Primary analysis population will include those subjects that have signed a PIC form, and have the CIP defined pacemaker implanted.

12.9 The Treatment of Missing, Unused or Spurious Data, Including Drop-Outs and Withdrawals

No imputation technique will be used, unless specified in the guidelines of the questionnaire data.

12.10 In Multi-Center Studies, the Minimum and Maximum Number of Subjects to be Included for each Center

This study is expected to enroll 2016 subjects in approximately 160 centers in the EMEA region and Asia-Pac region. It is desirable to have a balance of the subjects across participating centers; therefore, the maximum number of subjects to be included at each enrolling center is 200. Every effort will be made to promote recruitment; however, a low level of participation in the study could still occur, so the minimum number of subjects to be included at enrolling centers is one.

13.0 DOCUMENT RETENTION

The principal investigator (PI) will maintain all clinical study documents from prior, during and (as specified) after the clinical study on file at the site for a minimum of 15 years after the termination of this study, or longer as per local laws, or when it is no longer needed to support a marketing application, whichever is later.

The PI must contact the Sponsor prior to destroying or archiving off-site any records and reports pertaining to this study to ensure that they no longer need to be retained on-site.

All original subject files must be stored for the longest possible time permitted by the regulations at the hospital, research institute, or practice in question. If archiving can no longer be maintained at the site, the Investigator will notify the Sponsor.

All data and documents will be made available on request of the relevant authorities in case of an audit.

Ver. A

Study Name: BRADYCARE II

CIP

The Sponsor will archive and retain all essential clinical study documents from prior, during and (as specified) after the clinical study as per requirements.

14.0 AMENDMENTS TO CLINICAL INVESTIGATIONAL PLAN

Study related documents such as the CIP, CRFs, Informed Consent form and other subject information, or other clinical study documents will be amended as needed throughout the clinical study. The version number and date of amendments will be documented.

The amendments to the CIP and the subject's Informed Consent will be notified to, or approved by, the Ethics Committee and regulatory authorities, if required. Any amendment affecting study subjects requires that the subject be informed of the changes and a new consent be signed and dated by the Investigator and subject at the subject's next follow up visit.

15.0 STUDY COMMITTEES

15.1 STEERING COMMITTEE (SC)

The Steering Committee may be used to advise the Sponsor during a clinical study, such as in the development of the study CIP, during the conduct of the study, during data analysis and/or presentation/publication of the study results. Membership may include a Clinical Coordination Investigator (CCI) or site Investigators for the study under review.

16.0 INVESTIGATION SUSPENSION OR TERMINATION

16.1 Premature Termination of the Whole Clinical Study or of the Clinical Study in One or More Investigational Sites.

The Sponsor reserves the right to stop the study at any stage, with appropriate written notice to the Investigator.

Possible reasons for early termination of the study by the Sponsor, either at local, national or international level, may include, but are not limited to:

- The device / therapy fails to perform as intended
- Sponsor's decision
- Request from Regulatory bodies
- Request of Ethics Committee(s)
- Concern for subject safety and welfare
- Failure to secure subject Informed Consent prior to any investigational activity
- Repeated non-compliance with this CIP or the Clinical Trial Agreement
- Inability to successfully implement this CIP
- Violation of the Declaration of Helsinki 2008 (refer to Appendix C)
- Violation of applicable national or local laws and regulations
- Falsification of data, or any other breach of ethics or scientific principles

Study Name: BRADYCARE II

Ver. A

CIP

The study will be terminated according to applicable regulations.

The Investigator may also discontinue participation in the clinical study with appropriate written notice to the Sponsor.

Should either of these events occur, the Investigator will return all documents to the Sponsor; provide a written statement as to why the premature termination has taken place and notify the Ethics Committee and/or the Competent Authority (if applicable). Follow-up for all enrolled subjects will be as per CIP requirements.

A Principal Investigator, Ethics Committee or regulatory authority may suspend or prematurely terminate participation in a clinical study at the investigational sites for which they are responsible.

If suspicion of an unacceptable risk to subjects arises during the clinical study or when so instructed by the Ethics Committee or regulatory authority, St. Jude Medical may suspend the clinical study as appropriate while the risk is assessed. St. Jude Medical will terminate the clinical study if an unacceptable risk is confirmed.

St. Jude Medical will consider terminating or suspending the participation of a particular investigational site or Investigator in the clinical study if monitoring or auditing identifies serious or repeated deviations on the part of an Investigator.

If suspension or premature termination occurs, the terminating party will justify its decision in writing and promptly inform the other parties with whom they are in direct communication. The Principal Investigator and St. Jude Medical will keep each other informed of any communication received from Ethics Committee or regulatory authority.

If for any reason St. Jude Medical suspends or prematurely terminates the study at an individual investigational site, St. Jude Medical will inform the responsible regulatory authority, as appropriate, and ensure that the Ethics Committee are notified, either by the Principal Investigator or by St. Jude Medical. If the suspension or premature termination was in the interest of safety, St. Jude Medical will inform all other Principal Investigators.

If suspension or premature termination occurs, St. Jude Medical will remain responsible for providing resources to fulfill the obligations from the CIP and existing agreements for following up the subjects enrolled in the clinical study, and the Principal Investigator or authorized designee will promptly inform the enrolled subjects at his/her investigational site, if appropriate.

16.2 Resuming the Study after Temporary Suspension

When St. Jude Medical concludes an analysis of the reasons for the suspension, implements the necessary corrective actions, and decides to lift the temporary suspension, St. Jude Medical will inform the Principal Investigators, EC, or regulatory authority, where appropriate, of the rationale, providing them with the relevant data supporting this decision.

Concurrence will be obtained before the clinical study resumes from the Ethics Committee or regulatory authority where appropriate.

Study Name: BRADYCARE II

Ver. A

CIP

If subjects have been informed of the suspension, the Principal Investigator or authorized designee will inform them of the reasons for resumption.

16.3 Study Conclusion

The study will be concluded when:

- All sites are closed AND
- The Final Report generated by St. Jude Medical has been provided to sites or St. Jude Medical has provided formal documentation of study closure

17.0 PUBLICATION POLICY

The results of the clinical study will be submitted, whether positive or negative for publication.

A 'Publication Agreement' will be signed between the Principal Investigator and the Sponsor either as a separate Publication Agreement or within the Clinical Trial Agreement.

Ver. A

Study Name: BRADYCARE II

CIP

APPENDIX A: ABBREVIATIONS

Select or add abbreviations used

Abbreviation	Term
ADE	Adverse Device Effect
AE	Adverse Event
ANZ	Australia – New Zealand
ASADE	Anticipated Serious Adverse Device Effect
CA	Competent Authority
CCI	Clinical Coordination Investigator
CEC	Clinical Events Committee
CIP	Clinical Investigational Plan
CRF	Case Report Form
CPRB	Clinical Project Review Board
DD	Device Deficiency
DMP	Data Management Plan
DSMB	Data Safety Monitoring Board
EC	Ethics Committee
ECG	Electrocardiogram
eCRF	Electronic Case Report Form
EDC	Electronic Data Capture
EMEA	Europe, Middle East, Africa
GP	General Practitioner
IB	Investigator Brochure
ICMJE	International Committee of Medical Journal Editors
IRB	Institutional Review Board
ISB	Investigator Site Binder
ISO	International Organization for Standardization
MP	Monitoring Plan
NA	Not Applicable
PI	Principal Investigator
POA	Power of Attorney
RDC	Remote Data Capture
SADE	Serious Adverse Device Effect
SAE	Serious Adverse Event
SC	Steering Committee
SJM	St. Jude Medical
WMA	World Medical Association

Study Name: BRADYCARE II

Ver. A

CIP

